Statistical Analysis Plans	Data will be presented as mean \pm SEM for variables that are normally distributed, or median (IQR) for variables not normally distributed. Group means will be compared by ANOVA and post hoc tests except when data is normally distributed (a nonparametric analysis of medians will be performed using the Kruskal-Wallis test for non-normally distributed data). Chi-square tests or Fisher's exact tests will be used for incidence data. For analysis of microbiome taxonomic and functional data we will carry out Mann-Whitney-Wilcoxon matched pair tests for pairwise comparisons between time points. Unpaired Mann-Whitney-Wilcoxon tests will be used for pairwise comparisons between treatment groups. We will apply the Kruskal-Wallis test when more than two groups are compared. P values will be corrected for the total number of comparisons with false-discovery rate (FDR).

2. Introduction: Background and Scientific Rationale

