GOS and hGOS beneficially impact the gut microbiome, increasing beneficial bacteria (*Bifidobacterium* and *Akkermansia*) and saccharolytic potential of the microbiota and reduced intestinal permeability, modulating markers of inflammation⁹. Furthermore, GOS, but not hGOS, increased mucus in the intestinal lumen, suggesting different mechanisms of action. Our previous studies in mice have shown that short-term feeding of pure GOS increases expression of protective mucus-producing *MUC2*, decreases intestinal permeability, and reverses proportions of fecal β -galactosidases and β -glucosidases, reflecting increases in saccharolytic bacteria, including *Bifidobacterium*^{9, 25}.

In this trial, we will determine changes in the abundance of saccharolytic bacteria as described⁹. Briefly, we will use a reference study that mined 532 publicly available gut reference genomes and assigned them to four different groups (proteolytic, saccharolytic, lipolytic, and generalist bacteria) using metagenome analytical methods²⁶, and the metabolic reconstruction network AGORA²⁷. In the case that the genus is not categorized in the mentioned studies, will refer to the Bergey's Manual of Systematic Bacteriology and previously published reports.

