6.2 Assignment Procedures

Matching and Stratification:

N/A

Randomization, Concealment, and Blinding:

The Excel RAND function will be used for simple randomization of participants into the 3 different groups. The PI and designated study personnel are blinded to the randomization and are responsible for following the randomization and blinding procedures described in each clinical trial protocol.

Masking (Blinding):

This is a double-blinded study. The master randomization codes will be kept by IDS with appropriate security measures and access control. The research team will be unblinded once all of the samples have been collected and processed, before data analysis.

Unblinding. Circumstances for unblinding will be clearly established before the first patient begins treatment. Randomization procedures, if any, will be followed to ensure the code is broken only in accordance with the protocol. The study codes will be stored at the study site or may only be available directly from IDS. The code will only be broken in the case of an adverse event where it is necessary for the PI to know which treatment the individual is receiving before the individual can be treated. If it is

necessary to break the blind, the researcher will notify the IRB and document the event, together with the reasons for breaking the code.

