8.6. Variables Representing Treatment

A total of 45 individuals will be randomized 1:1:1 (placebo, GOS, hGOS) to treatment. Allowing for a 20% drop out rate, approximately 55 - 60 subjects will be enrolled.

9. Statistical Analysis Plans

a. Strategies that Apply to all the Specific Aims

- (1) To help ensure replicability of the research, the analysis plans will be reviewed and finalized prior to collection of data (a priori). For the specific aim, the analysis plan specifies detailed steps for obtaining estimates of population parameters (e.g intervention safety) and for making inferences.
- (2) Sensitivity analyses will be performed to assess the robustness of the major results as indicated by their sensitivity to reasonable perturbations of the choices of the methods and assumptions used. Any question about the optimal choice of methods and assumptions are best handled by relegating competing approaches to roles in the domain of sensitivity analyses. Results of the sensitivity analyses will be used to guide our level of trust in the main results. Best practices for dealing with incomplete data will depend on the documented causes of missing, censored, and coarsened values. The reasons for missing data values, drop-out, and protocol departures will have been documented in/with the database.
- (3) The plan also includes outcome-dependent exploratory analyses to generate new hypotheses.
- (4) Descriptive graphical and tabular methods will be used to characterize the participants, visualize the data, and examine relationships among variables.
- (5) To indicate precision, all statistical estimates of population parameters will be tabulated along with corresponding confidence intervals (CI) or standard errors (SE). The CI will be interpreted as the set of potential values of the population parameter that are most compatible with the observed data.
- (6) All hypothesis tests yielding p-values that are deemed to be not statistically significant will be reported as being inconclusive. The proposed statistical analysis strategy acknowledges that no p-value can reveal the plausibility, presence, truth, or importance of an association or effect-- which is consistent with the statements of the American Statistical Association [4,5], the recommendations in Nature [6,7], and guidance, such as the CONSORT Statement [1], STROBE Statement [2], and ICMJE guidance [3].²

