9.6. Missing data

We expect a 20% drop out during the proposed study. We assume the subjects will drop out randomly and all the missing data is missing completely at random (MCAR). In this case, we will implement complete-case analysis for the primary statistical analysis. However, we will also explore the possibility that the missing data is not MCAR. In the sensitivity analysis, we will compare the drop-out and non-drop group in terms of demographic characteristics and clinical factors. More specifically, we will perform two-group testing between the drop-out and non-drop group using either t-test, Wilcoxon test or chiq-square test depending on distribution and type of the variables of interest. If the missing data is indeed missing at random (MAR), we will perform multiple imputation method to generate the missing values with Rubin's rule to obtain the unbiased inference, which will be compared with results from the primary statistical results.

10. Safety Monitoring and Management

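### Section 6.2 ends the blind when samples are processed, not at database lock, so the last safety data and a few analyst judgements need not be final under the blind

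*Combined protocol and SAP*

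**What the plan says.** Section 6.2 states "This is a double-blinded study". The master codes are held by the Investigational Drug Services pharmacy, with provision for emergency code breaks. The planned end of the blind is then given: "The research team will be unblinded once all of the samples have been collected and processed, before data analysis".

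Section 4.3 takes blood and stool at Day 0 and Day 28. Sections 7.7 and 10.4 continue symptom ratings and AE recording to a contact one week after treatment, Day 35±2. Section 10.3 has the investigator grade the severity and relatedness of AEs. Section 11.8 provides for data queries but does not tie them to unblinding.

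On analysis, Section 9 part a promises that "the analysis plans will be reviewed and finalized prior to collection of data (a priori"). It also says "Best practices for dealing with incomplete data will depend on the documented causes of missing, censored, and coarsened values". Section 9.6 makes complete-case analysis primary and adds: "If the missing data is indeed missing at random (MAR), we will perform multiple imputation method to generate the missing values". Section 2.2 has a fallback for saccharolytic classification, opening "In the case that the genus is not categorized in the mentioned studies", which turns to a bacteriology manual and published reports.

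**The concern.** Blinding of the investigator protects two things: judgements made about participants while data are still being completed, and judgements made about the data before results are known. A trigger based on sample processing secures neither.

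The primary outcome is safety and tolerability, and part of it, the AE relatedness grade, is an investigator's opinion. If that opinion or an open query is settled after the arm is known, it can lean toward or away from the prebiotic without anyone intending it. The same applies to deciding whether an unclassified genus counts as saccharolytic, or whether a participant's data are set aside, once it is known which arm the choice favours. At stake is the credibility of the relatedness table and of the biosignature conclusion in a trial that describes itself as double-blind.

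**Working it through.** The plan attaches no figure to this rule, so there is none to reproduce. The check compares what the trigger covers with what remains open.

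| Item | Section | Latest planned time | Must be final before unblinding? |
|---|---|---|---|
| Blood and stool | 4.3, 7.6 | Day 28±2; stool may be mailed back later | Yes |
| Symptom ratings | 7.7, 10.4 | Day 35±2 | No |
| AE recording | 7.7, 10.3 | Day 35±2 (seven days after last dose) | No |
| AE severity and relatedness | 10.3 | No completion date tied to unblinding | No |
| Data queries | 11.8 | None given | No |
| Database lock | Not mentioned | – | No |
| Uncategorised genera | 2.2, 9.2 | None given | No |
| Incomplete-data handling | 9 part a, 9.6 | Depends on observed causes | No |
| Data exclusions | 7.8 only in part | None given | No |

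On the last row, 7.8 removes participants who discontinue early from Objective 2. Section 9 does not say how participants who continue on a reduced dose (6.7, 10.2, 10.4) enter Aim 2.

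**How many Day 35 contacts could be outstanding?**

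1. Interval from final visit to follow-up contact: nominally 35 − 28 = 7 days. With the windows, the shortest is (35 − 2) − (28 + 2) = 3 days and the longest (35 + 2) − (28 − 2) = 11 days.
2. Accrual: the synopsis gives 40 weeks to complete enrolment. Enrolment is 48 in the synopsis and 60 in 9.5, so 48/40 = 1.2 to 60/40 = 1.5 per week, if even.
3. Participants inside that interval when the last sample is taken: 1.2 × 7/7 = 1.2 to 1.5 × 7/7 = 1.5 nominally, and 1.2 × 11/7 = 1.9 to 1.5 × 11/7 = 2.4 at the widest.

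That is about one or two participants, and it assumes the last samples are processed at once. The term for processing is not defined. If processing takes more than 11 days after the last final visit, no contact made within its window is outstanding. The count covers contacts only: an ungraded AE or unresolved query could belong to any participant.

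**The case against.** The strongest reply is that the plan is largely fixed already. Section 9 part a commits to finalising it before data collection. Section 9.2 names matched-pair Wilcoxon and Kruskal-Wallis tests for the microbiome, and paired t-tests and ANOVA for biomarkers and zonulin. Section 9.6 makes complete-case analysis primary and imputation a sensitivity analysis. Aim 1 is descriptive and rests mainly on participants' own symptom reports, collected weekly under the blind. Mailed stool and sequencing may well push unblinding past Day 35. Most of this stands, and it is why the exposure is modest. It does not close the gap, because none of it sets when AE grades, queries, genus assignments or exclusions must be final.

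It can also be said that a genus classification applies equally to every arm. True, but someone who sees abundances by known arm can still see which classification helps the prebiotic. The discretion is confined to uncategorised genera.

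A reader might infer that early unblinding raises the false-positive rate by a calculable amount. Simulated null trials with 16 per arm give 5.9% to 6.5% when the smaller of the ANOVA and Kruskal-Wallis p-values is reported, against an assumed nominal 5%. Adding two log-scale analyses gives about 9% to 10%. Those figures do not measure this problem. The tests compare all three arms at once, and their p-values do not change when arms are relabelled, so an analyst with masked labels could make the same choice. The log-scale analyses are not in the plan, and the rates ignore its false-discovery-rate correction.

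A reader might also take the synopsis wording, "Group means will be compared by ANOVA and post hoc tests except when data is normally distributed", as proof that the biomarker test is open. It conflicts with 9.2, but reconciling the synopsis, 9.2 and 9.5 is a separate point that masking would not solve. The statement "The plan also includes outcome-dependent exploratory analyses to generate new hypotheses" concerns work labelled as hypothesis-generating and does not make the main tests open.

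**Conclusion.** The point holds as a gap in a stated rule. Section 6.2 unblinds the research team on sample processing and before analysis, while the last safety contact, AE grading, query resolution and a few analyst judgements are not required to be complete. No size of bias can be derived from the documents. The only quantity available is the one or two participants whose Day 35 contact might be outstanding, which assumes even accrual over 40 weeks and immediate processing.

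The documents do not show that the primary outcome is generally compromised. The study team stays blinded through the weekly contacts for nearly everyone, and any unblinded safety look belongs to the medical monitor (6.7, 10.2). The conclusion assumes that no lock or masked analyst is specified elsewhere; Section 11.5 on key roles was not available to check. It is a cheap improvement, not a defect that threatens the trial.

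**What to change.** In 6.2, replace the sentence that sets the unblinding trigger with:

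> The research team will be unblinded only after the last Day 35 contact, completion of AE severity and relatedness grading, query resolution and documented database lock. The list of saccharolytic genera and any data exclusions will be finalised before unblinding, and the main A1/A2 tables will first be produced on masked labels (A/B/C) supplied by the pharmacy.

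Leave emergency and medical-monitor unblinding as written.

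The pharmacy already holds the codes, so the cost is one masked code file and possibly a short delay to unblinding. Masking may be imperfect: if *Bifidobacterium* rises on the prebiotics as expected, abundance tables could reveal which label is placebo. For that reason the genus list and exclusions should be settled before any table by arm is run.

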6.3. Intervention – Procedural (if applicable)

Description:

- (1) Subjects will receive enough prebiotic or control powder for the complete 28 days in pouches containing the exact daily dose. An additional pouch will be provided for both the 5g and 7.5g quantities in case of loss or spillage. The powder can be added to hot or cold non-alcoholic beverages or sprinkled over food.
- (2) Subjects in the study will consume 5 grams of either GOS, hGOS or placebo twice daily on days 1–10 followed by 7.5 grams twice daily on days 11–28¹⁰.

Training on Procedural Intervention:

Participants will be provided with detailed instructions of how to prepare and consume the prebiotics or control powder. Individuals will be informed on the potential side effects and how to avoid them by rationing the treatment over the day if needed or chosen.

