Obtain informed consent. Screen potential participants by inclusion and exclusion criteria; obtain medical history, document. **Total N = 48**

Visit 1

Time Point

Weekly GSSC data collection

Visit 2
Time Point

4 weeks: collect blood and stool. Administer 38-point Gastrointestinal Symptom and Severity Checklist (GSSC) Questionnaire (FFQ)

Analyses: (a) Evaluation of inflammation and intestinal barrier function in serum; (b)

4.1.Treatment Design

Dose rationale. The intervention will include a dose ranging between 10 to 15 g daily as previously reported¹⁰. Doses were selected based on previous literature reports^{16, 17, 28-30} and the interventions conducted by our group to assess efficacy of GOS in lactose-intolerant individuals^{10, 11, 31, 32}. The hGOS preparation will be composed of GOS enriched with LacNac at a concentration of 6.7-31 μ g/mL (<1% of the formulation), which is in the range found in human breast milk³³ and hence considered safe.

Regimen. The prebiotics dose will be 5 grams twice daily on days 1–10 followed by 7.5 grams twice daily on days 11–28. The placebo (powdered corn syrup comprised of fructose, glucose, and an inert cellulose material that matched the consistency, color, sweetness, and taste of the prebiotics) will be administered in a blinded matching packet at the same doses. If participants miss taking a dose on a given day, they will be directed to put the pouch for that day aside, and on the next day take the next numbered pouch.

4.2.Experimental / Observational Design

Subjects will be assigned randomly to one of 3 groups (n = 16): GOS, hGOS or placebo.

4.3.Measurement Design

Blood and stool samples will be collected at baseline (Day 0) and end of treatment (Day 28). Stool collection kits will be provided to participants in case samples cannot be obtained *during study visits*. Safety and tolerability will be determined based on the severity and/or frequency of side effect using a 38-point Gastrointestinal Symptom and Severity Checklist (GSSC). In addition, tolerability will be evaluated through occurrence of drop-out and adherence.

Measurements on blood (10 mL per visit for a total of 20 mL):

- (1) Fasting venous blood samples will be drawn and serum will be used to quantify zonulin using the Zonulin (IDK® Zonulin) (Serum) ELISA test (Immundiagnostik AG).

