Where the K_m factor is a number based on body surface area. In our animal study we used a dose of 1,500 mg kg⁻¹, based on ~30 mg LacNAc fed to a ~20 g mouse per day²⁵. We used a K_m factor of 3 for mice and 37 to represent a 60 kg human adult.

We can consistently produce hGOS containing concentrations that exceed 25 g/L of LacNAc with no significant variation between batches observed. Therefore, our approach is to normalize to reach the proposed dose levels using pure GOS. The active component is in power form that will be obtained after lyophilization. Concentration will be confirmed using previously developed HPLC protocols³³

Acquisition: [name], Professor of Plant and Microbial Biology at North Carolina State University and Co-investigator in this proposal, will coordinate with the Golden LEAF Biomanufacturing Training and Education Center (BTEC) the cGLP production of the prebiotics galacto-oligosaccharides (GOS) and GOS enriched in N-acetyl-D-lactosamine (LacNac, humanized GOS, hGOS) for the clinical intervention planned for the study. BTEC has the capabilities, equipment, and expertise for the bioprocess cGLP production (See Appendix 1).

Formulation/Packaging/Labeling: GOS, hGOS, and placebo will be supplied as a sterile powder by BTEC, dried and portioned into daily dose pouches under sterile conditions at the NC Food Innovation Lab, Kannapolis, NC, . Pouches will be labeled and will serve to protect the preparations from light, air,

Protocol Number:
Study Acronym: GOS Pilot

Enrollment ID:

Lot No.:

Subject Number:

Subject's Initials:

Date Dispensed:

Contents: 56 pouches, 5 g each for the first 10 days followed by 7.5 grams each for days 11-28 of GOS, hGOS or matching placebo, plus two additional packets (one 5mg and one 7.5mg) for inadvertent loss or spillage.

Directions: Use only as directed. To be taken by mouth with food or beverage.

This product is an investigational product to be dispensed only by a qualified investigator.

Storage: Room Temperature 15-30 °C (59-86°F)

Caution: New drug limited by law to investigational (clinical trial) use only. Keep out of reach of Children.

Manufactured By: Golden LEAF Biomanufacturing Training and Education Center (BTEC), [name]

Distributed by:

and moisture. Product will then be transferred to the UNC Investigational Drug Services (IDS).

Storage and Stability:

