The powder prebiotics galacto-oligosaccharides (GOS), GOS enriched in N-acetyl-D-lactosamine (LacNac, humanized GOS, hGOS), and placebo can be safely stored in a dry area at room temperature and hold an expiration date of 2 years after production.

Preparation and Administration: Individuals will be provided with a total of 58 pouches numbered by day (#1 to #56) containing the appropriate daily dose of treatment or placebo. Pouches 57 and 58 will be extra pouches in case of loss or spillage. Participants will be instructed to consume one pouch twice a day. The premeasured powder can be added to hot or cold non-alcoholic beverages or sprinkled over food.

Modification: Individuals experiencing more than three of the following side effects a day: bloating, flatulence, belching, abdominal pain, discomfort, watery stool, and vomiting will be instructed on how to spread out the daily dose to minimize side effects. Participants experiencing these side effects be asked about frequency and severity. Severe side effects interfering significantly with subject's usual function will result in withdrawal from study. Weekly phone contacts will allow for timely report of adverse effects. Participants will also be given the choice to contact the study PI directly in case of emergencies.

Accountability: UNC Investigational Drug Services (IDS) will keep source documentation for accountability of the study treatments that will detail receipt, dispensing, and return of used and unused prebiotics and placebo. Treatment products will be stored in locked facilities until they are either returned to the PI at the end of the study. Prior to dispensing, sachets containing the treatment will be visually inspected. If the package appears to have tears or sign of tampering, the sachet will be rejected for use but retained until the end of the study. At the end of the study, the study team will determine dispensation of all remaining unused treatment packs at the study site. An accountability log will be kept, indicating the final disposition of study treatment. This log will be provided to the PI at the end of the study.

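### Sections 6.1 and 6.3 describe each pouch as a full day's dose, which conflicts with the label, the pouch count and the gram regimen; the spare-pouch units and the missed-dose sentence do not fit either.

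*Combined protocol and SAP*

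**What the plan says.** Three places describe a pouch as one day's dose. The packaging text in Section 6.1 has the product "portioned into daily dose pouches under sterile conditions". The administration text in Section 6.1 provides "58 pouches numbered by day (#1 to #56) containing the appropriate daily dose of treatment or placebo". Section 6.3 supplies the powder "in pouches containing the exact daily dose".

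Other text points to half a day's dose per pouch. The administration paragraph continues: "Participants will be instructed to consume one pouch twice a day". The label in Section 6.1 reads: "Contents: 56 pouches, 5 g each for the first 10 days followed by 7.5 grams each for days 11-28". Sections 2.3, 4, 4.1 and 6.3 all give the regimen as 5 g twice daily on days 1 to 10 and 7.5 g twice daily on days 11 to 28. Section 2.3 also states it as 10 g/day rising to 15 g/day.

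The label lists the two spare packets as "one 5mg and one 7.5mg", whereas Section 6.3 gives the spares in the 5 g and 7.5 g sizes. A similar slip appears in the dose-reduction text: Section 10.2 refers to a 7.5 mg sachet and Section 10.4 to a 7.5 g sachet.

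After a missed dose, Section 4.1 tells participants to "put the pouch for that day aside, and on the next day take the next numbered pouch". Section 6.6 monitors adherence by the self-reported number of pouches left, and Section 8.1 lists adherence as a tolerability parameter.

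**The concern.** The conflicting phrases sit in the packaging, label, administration and procedural text, not in background. According to Section 6.1, powder is produced at one facility, portioned into pouches at a second and dispensed through a third, so each step depends on the written description. Specific Aim 1 is the tolerability of a stated daily dose, so what a pouch holds and how many are taken per day should admit only one reading.

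The missed-dose sentence matters because the pouches are numbered and change size partway through. If the numbers slip against the days, the change from 5 g to 7.5 g pouches no longer falls cleanly on day 11, and a count of pouches left no longer shows which doses were missed.

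**Working it through.** **Inputs.** Days 1 to 10 (10 days) and days 11 to 28 (18 days); two pouches per day (Section 6.1); 5 g and 7.5 g per pouch (label); 10 and 15 g/day (Section 2.3); 56 pouches plus 2 spares (Section 6.1).

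**The plan's own count.** Pouches = 2 × (10 + 18) = 56; with the spares, 56 + 2 = 58. This reproduces the stated figures. At two per day, the first 2 × 10 = 20 pouches cover days 1 to 10 and the other 2 × 18 = 36 cover days 11 to 28.

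**Intake under each reading.** Daily dose = pouches per day × grams per pouch. Total = the sum over the two periods.

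| Reading | g/day | Total over 28 days | Pouches needed |
|---|---|---|---|
| Label content, two per day | 2 × 5 = 10, then 2 × 7.5 = 15 | 20 × 5 + 36 × 7.5 = 370 g | 56 |
| Daily-dose pouch, two per day | 2 × 10 = 20, then 2 × 15 = 30 | 20 × 10 + 36 × 15 = 740 g | 56 |
| Daily-dose pouch, one per day | 10, then 15 | 10 × 10 + 18 × 15 = 370 g | 28 |

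The first row matches the gram regimen, the label and the count together. The second matches the count but not the gram regimen or the label, and is 740 / 370 = 2 times the first. The third matches the daily dose but not the count, the label or the twice-daily instruction.

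**Units.** 5 g / 5 mg = 5,000 mg / 5 mg = 1,000; the ratio for 7.5 g and 7.5 mg is the same. This is a separate conflict and plays no part in the factor of 2.

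**Numbering.** Numbering by day from 1 to 56 does not fit 28 days. At two per day, day *d* uses pouches 2*d* − 1 and 2*d*.

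**Missed dose, worked example.** Suppose pouch 3, the first of day 2, is missed.

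- Literal reading of Section 4.1: pouch 3 is set aside and pouch 4 is taken on day 3. From then on day *d* uses pouches 2*d* − 2 and 2*d* − 1. Day 10 uses 18 and 19. Day 11 uses 20 (5 g) and 21 (7.5 g), which is 12.5 g. Day 28 uses 54 and 55. Pouches 3 and 56 remain.
- Reading a dose as a single pouch: pouch 3 is set aside and pouch 4 is taken later on day 2 as scheduled. The numbering stays aligned, day 11 uses 21 and 22 (15 g), and only pouch 3 remains.

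The same event therefore leaves one or two pouches, and day 11 is either 12.5 g or 15 g. If the second pouch of a day is the one missed, both readings agree.

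**The case against.** The best case against the point is that the protocol largely corrects itself. The gram regimen is the same in all four places. Every pouch or sachet size given in grams is 5 g or 7.5 g, including in the dose-reduction text of Sections 6.7 and 10.4, and no section describes a 10 g or 15 g pouch. Section 6.3 gives the spare sizes in the sentence after the disputed phrase and then states the twice-daily regimen. On this view the daily-dose wording is loose shorthand for the day's supply, and the milligram entry is a typing slip on a line that gives the other 56 pouches in grams. A missed dose can also mean a single pouch, and the adherence denominator of 56 at two per day is clear. Finally, Section 6.3 promises participants separate detailed instructions, which are not in the documents and may be worded correctly.

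Most of this stands. A reader might infer that the protocol permits 20 then 30 g/day, or that participants were exposed to twice the stated dose. The documents do not support that: it needs a pouch size that appears nowhere, and it contradicts the regimen, the label and the tolerability objective. Nor does the milligram entry add to it.

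The objection does not remove the contradictions. Agreement among the other parts shows which phrases are out of line, but those phrases remain in the text that governs filling and administration. The gram regimen also repairs neither the label unit nor the missed-dose sentence.

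**Conclusion.** The point holds as an internal inconsistency in the description of the product. Its parts differ in weight:

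- **Pouch content.** Three statements are each out by a factor of 2 against the label content and the regimen, and the by-day numbering does not fit 28 days. The factor becomes a difference in intake only if someone fills pouches to the daily-dose wording and they are then taken twice a day.
- **Units.** There is a 1,000-fold conflict on the label for the two spares, and a similar one between Sections 10.2 and 10.4.
- **Missed doses.** The instruction is ambiguous when the first pouch of a day is missed. One such event can move the numbered step by one pouch and leave two pouches instead of one. This assumes that pouches are numbered consecutively, two per day, with the size change after pouch 20.

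This should be corrected, because it concerns operative dosing text in a tolerability study. It is not evidence of a wrong regimen or of harm. Which content, reduced dose or missed-dose rule is right is not decided here.

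**What to change.** Before packing and labelling, the sponsor should reconcile Section 4.1 (missed dose), Section 6.1 (packaging, label and administration) and Section 6.3, so that content per pouch, pouches per day, pouch numbering, units and the missed-dose instruction all agree. The units in Sections 10.2 and 10.4 should be aligned in the same pass, and the separate participant instructions checked against the result. The missed-dose sentence should cover a missed first pouch, a missed second pouch and a wholly missed day.

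The adherence measure in Section 6.6 should then be defined from the reconciled count: pouches taken divided by pouches due to date, stating whether the two spares are counted.

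The cost is a wording amendment and a label check, with no change to the design, sample size or analysis. If packing has already been done, the content and label of the packed pouches should be verified and recorded.
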